#### **4.5 Participant Withdrawal or Discontinuation from Study Procedures/Intervention**

All study participants are free to withdraw or discontinue from study procedures or the intervention. The power calculations account for 15% to 25% participant attrition, though the actual attrition rate is expected to be much lower based on previous studies in the YK Delta that have had attrition as low as 3%.

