## SAMPLE SIZE CONSIDERATIONS

There are about 127, 175, and 108 children ages 1 to 11 years in communities A, B, and C respectively. Some are siblings or relatives living in the same home. Based on a survey of 123 households in the 3 study communities, for the power calculations, each household was assumed to have an average of  $2.15 \pm 1.23$  children per household. In addition, to account for the clustering of children within households, a conservative intra-family correlation (IFC) of 0.3 was assumed, but an IFC as high as 0.5 was assumed to assess the effect on power (Eldridge et al. 2006).

Participation in previous studies has been over 60%. Based on our pilot study, it is feasible and reasonable to enroll at least 50% of eligible children. Communities A and B will be in the intervention arm (expected N=136) and community C will be in the control arm (expected N=56). For the power determination, a 15% to 25% attrition rate was estimated by 6 months, but it is expected that actual attrition will be less than 10% by the 6-month follow-up.

Power is determined for comparing the average reduction from baseline to 6 months between children in the intervention arm and no-treatment control arm for the primary outcome: added sugar intake per day (determined by hair samples). Based on pilot data from 54 Yup'ik children ages 6 to 17 years, the mean $\pm$ SD baseline added sugar intake, as measured by hair samples, is expected to be  $193.0 \pm 43.6$  grams per day. (Chi et al. 2015). A correlation of 0.6 is assumed between the measures at baseline and 6 months to determine the standard deviation for reduction from baseline to 6 months.

The power is calculated using a 2-sided significance level of alpha=0.025 to control the type I error for the testing of the primary outcome, and using a 2-sample t-test to compare the average reduction between the intervention arm and no-treatment control arm using the expected (unequal) sample sizes and adjusted for the IFC and attrition (Eldridge et al. 2006).

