The expected numbers of children in the intervention arm and control arm will provide adequate power to test secondary hypotheses about a sustained reduction in sugared fruit drink intake and added sugar intake 6 months after the end of the intervention for children in the intervention arm. Based on a 2-sided 0.05 significance level, the power is >80% to detect a difference of 0.60 standard deviation units in the change from baseline to 12 months between the two arms. For example, power is 88% to demonstrate an intervention effect for a 20% reduction in the intervention arm versus a 2% reduction in the control arm for added sugar intake. The expected number of caregivers in the intervention arm is N=51 and in the control arm is N=21, and these sample sizes also provide adequate power to the test secondary hypothesis about a greater reduction in added sugar intake at the end of the intervention for caregivers in the intervention arm as compared to the control arm. Based on a 2-sided 0.05 significance level, the power is >80% to detect a difference of 0.75 standard deviation units in the change from baseline to 6 months between the 2 arms. For example, power is 81% to demonstrate an intervention effect for a 25% reduction in the intervention arm versus a 5% reduction in the control for the caregiver's added sugar intake.

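### The claim of more than 80% power for a 0.60 SD difference at 12 months is not met within the plan's own 15% to 25% attrition range, and no 12-month attrition is stated

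*Combined protocol and SAP*

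**What the plan says.** Sample Size Considerations gives the 12-month power for children as follows: "the power is >80% to detect a difference of 0.60 standard deviation units in the change from baseline to 12 months". The test behind it is two-sided at 0.05. An example follows, of 88% power for a 20% reduction against a 2% reduction. The paragraph does not say which IFC, attrition rate or correlation lies behind either figure.

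The inputs stand earlier in the same section, where they are set out for the primary 6-month comparison:

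- 136 children expected in the intervention arm and 56 in the control arm;
- 2.15 ± 1.23 children per household, from a survey of 123 households;
- on clustering, "a conservative intra-family correlation (IFC) of 0.3 was assumed", with 0.5 as a check;
- on loss, "a 15% to 25% attrition rate was estimated by 6 months", although actual loss by then is expected to be under 10%;
- a two-sample t-test with unequal arms, adjusted for the IFC and attrition.

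Section 4.5 repeats the attrition range without a time point: "The power calculations account for 15% to 25% participant attrition". Section 13.1 sets a goal of retaining more than 75% of those enrolled.

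**The concern.** The 12-month statement is in SD units, so it can be checked from sample sizes, clustering and attrition alone, without any view on the SD of the change. The stated inputs do not appear to reach 80%. The one attrition range with a date attached stops at 6 months, while the claim is about 12.

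The statement supports the second hypothesis in section 11.1.2, that the reduction is sustained 6 months after the intervention ends. If power is overstated, a null 12-month result will be read as stronger evidence against a lasting effect than the design can give.

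**Working it through.** **Design effect.** The plan gives a household-size SD, and the methods paper it cites is titled for the coefficient of variation of cluster size. The matching form is DE = 1 + [(1 + CV²)m − 1] × IFC.

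- CV = 1.23/2.15 = 0.572, and CV² = 0.327.
- (1 + 0.327) × 2.15 = 2.854.
- IFC 0.3: DE = 1 + 1.854 × 0.3 = 1.556.
- IFC 0.5: DE = 1 + 1.854 × 0.5 = 1.927.

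**Does this form reproduce the plan's own table?** I took the four rows of the 6-month table that are below 99%, at both IFC values, plus the 88% example. That makes nine figures. I left the SD of change free, because only the pattern matters here. The varying-size form matches all nine to within about 0.5 point (sum of squared errors about 0.5). At 15% attrition the fit is:

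| Reduction, intervention vs control | Stated (IFC 0.3 / 0.5) | Fitted |
|---|---|---|
| 30% vs 5% | 98 / 95 | 98.2 / 95.0 |
| 20% vs 1% | 86 / 76 | 85.5 / 76.2 |
| 30% vs 10% | 89 / 81 | 89.1 / 80.8 |
| 20% vs 2% | 81 / 71 | 81.2 / 71.2 |
| 20% vs 2%, alpha 0.05 (12 months) | 88 | 88.0 |

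The simple form, 1 + (m − 1) × IFC = 1.345 at IFC 0.3, misses several figures by 1 to 1.7 points (sum of squared errors about 12), because it cannot produce the gap between the two IFC columns. The table therefore points to the varying-size form.

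The fit is equally good at 15%, 20% or 25% attrition, with SDs of 51.1, 49.5 and 47.9 g, so the table does not reveal the attrition used. None of these SDs enters the next step.

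**Power for 0.60 SD.** With attrition a, the effective sizes are n₁ = 136(1 − a)/DE and n₂ = 56(1 − a)/DE. The noncentrality is 0.60 × √[n₁n₂/(n₁ + n₂)], and the test is a two-sided 0.05 t-test on n₁ + n₂ − 2 degrees of freedom.

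For example, at 15% attrition and IFC 0.3, n₁ = 115.6/1.556 = 74.3 and n₂ = 47.6/1.556 = 30.6. The noncentrality is 0.60 × √21.67 = 2.793, which gives 79.0% power.

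| IFC | Attrition | Effective n | Noncentrality | Power | SD detectable at 80% power |
|---|---|---|---|---|---|
| 0.3 | 15% | 74.3 / 30.6 | 2.793 | 79.0% | 0.61 |
| 0.3 | 20% | 69.9 / 28.8 | 2.710 | 76.5% | 0.63 |
| 0.3 | 25% | 65.5 / 27.0 | 2.623 | 73.7% | 0.65 |
| 0.5 | 15% | 60.0 / 24.7 | 2.510 | 69.9% | 0.68 |
| 0.5 | 20% | 56.5 / 23.3 | 2.435 | 67.2% | 0.70 |
| 0.5 | 25% | 52.9 / 21.8 | 2.358 | 64.3% | 0.72 |

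A normal approximation is slightly kinder at IFC 0.3 (79.8%, 77.3% and 74.6%) but still below 80%. At 10% attrition the t-test gives 81.3%. Power equals 80% at 12.9% attrition, or 14.5% by the normal approximation.

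**The 12-month inputs.** The stated 88% is matched by the same effective sizes and SD as the 6-month table, with only alpha changed from 0.025 to 0.05. No further allowance for loss after month 6 is visible.

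**The case against.** The best defence is that the claim is nearly right. At 15% attrition it misses by one point by the t-test and by a fraction of a point by the normal approximation. At the loss the plan actually expects, under 10% by 6 months, power is at least 81.3%. Both statements are true. But section 4.5 and Sample Size Considerations both say the power calculations use 15% to 25%, and the figure should hold somewhere in that range.

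A second defence is a smaller design effect. The simple form gives 84.6% at 15% attrition, 82.4% at 20% and 79.8% at 25%. If lost children are spread across households, so that mean household size shrinks with attrition, the figures are 82.4%, 81.2% and 79.9%. Neither option fits the 6-month table as well: the shrinking-household variant has squared errors of 4.4 to 11.8, against 0.5. The plan also says it assumed 2.15 children per household. This remains an inference about method, because the design-effect formula is not written out.

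Three stronger readings are tempting, and the documents do not support them.

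- **A single true figure of about 76%.** That needs 20% attrition, which the plan never names. The caregiver sizes of 51 and 21 do fit 20% (136 × 0.80/2.15 = 50.6 and 56 × 0.80/2.15 = 20.8), but they belong to a different outcome, and the children's table fits 15% or 25% equally well.
- **A conflict between the 88% example and the 0.60 SD statement.** The example is a difference of 0.18 × 193 = 34.7 g. That is 0.89 SD with the 39.0 g implied by the stated SD and correlation (43.6 × √0.8), or 0.68 to 0.73 SD with the SDs that fit the table. Either way it is a larger effect with higher power, which is compatible with a threshold at 0.60 SD.
- **That the plan ignores loss between 6 and 12 months.** Section 4.5's range has no date and could cover the whole study. All that can be said is that the 12-month attrition is not stated.

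**Conclusion.** The concern holds in a limited form. With the plan's own sample sizes, household-size distribution and attrition range, power for 0.60 SD at 12 months is about 74% to 79% at IFC 0.3 and about 64% to 70% at IFC 0.5. The claimed level is not reached anywhere from 15% to 25% attrition. The gap to 80% is about 1 point at the favourable end and about 6 points at the other, at IFC 0.3.

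This rests on the varying-cluster-size design effect, which the plan's inputs and its 6-month table both point to, and on household size staying at 2.15. It does not rest on any SD of change. If section 4.5's range is read as covering 12 months, these figures apply directly. If loss by month 12 goes beyond 25%, power is lower still, for example 70.7% at 30%. The consequence is modest: a secondary hypothesis is affected, and neither the sample size nor the analysis depends on the figure.

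**What to change.** In Sample Size Considerations, replace the 12-month statement with one of two equivalent forms at two-sided 0.05 and IFC 0.3: about 74% to 79% power for 0.60 SD at 25% to 15% attrition, or 80% power for about 0.61 to 0.65 SD at 15% to 25% attrition. Give the IFC 0.5 results alongside, as the primary table does: about 64% to 70% power for 0.60 SD, or 80% power for about 0.68 to 0.72 SD.

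State the attrition assumed by 12 months, and write out the design-effect formula so that a reader can reproduce the figure. If the sponsor prefers to keep the stated power for 0.60 SD, the text should say that it assumes attrition below about 13% at 12 months.

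The cost is a few lines of text. No children are added, and the design and analysis do not change.

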## PLANNED INTERIM ANALYSES (IF APPLICABLE)

No interim analysis is planned for stopping the study early

### 13.1 Final Analysis Plan

The analysis will be based on the intent to treat principle. Demographic variables will be summarized for the intervention arm and no-treatment arm at baseline and at each follow-up for all outcome measures and behavioral survey variables, as well as baseline demographics. Quantitative measures will be summarized by the mean and standard (or median and interquartile range for measures with a skewed distribution) and categorical measures will be summarized by frequency and percentage.

Linear regression analyses will be used to test if the average change in added sugar intake between baseline and 6 months is the same for children in the intervention arm and no-treatment control arm. A 2-sided 0.025 significance level will be used for the tests of the primary outcome. Generalized estimating equation (GEE) methodology will be used to fit the linear regression models using robust standard errors that account for potential clustering of outcomes within a household and allow for heteroscedasticity (Hardin and Hilbe 2003). Additional linear regression analyses will compare the 2 arms adjusted for baseline characteristics to assess for potential confounding and to assess for moderation of the intervention effect on child sugar intake by baseline characteristics, including child age, child sex, and traditional diet. In addition, to assess the effects of sex as a biological variable, separate estimates for the intervention effect on added sugar intake will be reported by child sex.

Similar linear regression analyses will be performed for the secondary outcomes for changes in caregivers' added sugar intake, knowledge, beliefs and self-efficacy. Outcomes at 1 month and 3 months will be summarized to elucidate the changes from baseline to 6 months in the intervention arm and no-treatment arm. Linear regression analyses will also be used to test the exploratory hypothesis that children in the intervention arm will have decreased sugared fruit drink intake after having received the intervention (at 6 months and 12 months).

A secondary hypothesis is that greater improvements in caregiver knowledge, beliefs, and self-efficacy in the intervention arm as compared to the no-treatment control will result in sustained reductions in sugar fruit drink intake and added sugar intake for children in the intervention arm 6 months after the intervention ends. This will support the hypothesis that behaviors are the mechanisms by which sugared fruit drink intake and added sugar intake are reduced. To assess this hypothesis, we will use linear regression analysis to test if the average change in added sugar intake between baseline and 12 months is the same for children in the intervention arm and no-treatment control arm. Mediation analysis will then be used to assess if changes between baseline and 6 months in caregiver's knowledge, beliefs, and self-efficacy mediate the change between baseline and 12 months in children's sugar intake. The initial mediation analyses will follow the traditional approach of Baron and Kenny (1986) but the formal test for mediation will be based on a product of coefficients approach that directly tests for a

non-zero indirect effect using a bias-corrected bootstrap confidence interval (Hayes 2013). The test for mediation will be done for each mediator individually and for all mediators as a group.

Missing data will be managed as described in Strategies for Recruitment and Retention. Information will be collected on the reasons for discontinuation and withdrawal from the study. This information will be used to assess whether there is non-ignorable nonresponse. In the case of non-ignorable nonresponse, the method of Rotnizky et al. (1998) based on augmented inverse probability of censoring weighted estimating equations, will be used to perform a sensitivity analysis to examine how the estimated intervention effect on the primary outcome measures changes over a range of plausible values for the nonresponse mechanism. Otherwise, multiple imputation methods will be used to account missing outcomes and to derive intervention effect estimates consistent with the intent to treat principle (Schafer 2005). The goal of the study is to retain >75% of those enrolled. Statistical analysis will be performed using SAS Version 9.4 (SAS Institute Inc., Cary, North Carolina) and R version 3.5 (R Foundation for Statistical Computing, Vienna, Austria).

To assess the hypothesis that children in the intervention arm will have an altered oral microbiome, due to changes in sugared fruit drink and added sugar intake, data from a microbiome analysis of oral plaque samples collected at five data collection timepoints (baseline, 1 month, 3 month, 6 month and 12 month) will be used to compare changes in mutans streptococci levels and other oral microbiome features (e.g., species abundance, composition and diversity). Linear and log-linear regression will be used to test separately if there are changes in mutans streptococci levels and other oral microbiome features and to compare changes in children in the intervention versus control communities. Robust standard errors will be used with linear regression and log-linear regression to account for potential heteroscedasticity and overdispersion.

Similar analyses will be conducted on the 3m and 6m data collected from families in the control community who receive the modified intervention.

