## STUDY DESIGN

This is a 2-arm community-based behavioral trial. Participants, interventionists, investigators, and outcomes data collection staff will not be masked because it is not feasible. Data processors will be masked. While attempts will be made to mask the analyst, it will likely not be effective because of the different sizes of the intervention and control groups.

There is a total of 3 study communities (2 in the intervention arm and 1 in the no-treatment control arm). The 3 communities are located in Alaska's YK Delta, about an hour by airplane from Bethel. The 2 communities in the intervention arm are about 15-minutes away from each other by airplane. The community in the control arm is about 45 minutes away from the 2 communities in the intervention arm, which will help to minimize contamination between the control and the 2 treatment arms.

Two communities will be in the intervention arm and one community in the control arm. Allocation to the intervention arm was based on the order in which communities were ready to participate in the study as assessed during recruitment of communities. Randomizing at the community-level would have required a sample size that is beyond the scope of the current study budget. Randomizing at the family- or child-levels would not have been possible because of the small size of study communities and high risk of contamination between families or among children from the same family.

The focus is on Yup'ik Alaska Native communities because of the high rates of added sugar intake and tooth decay. Children are the focus of the primary outcome measure based on the potential for a lifetime of benefit associated with reduced added sugar intake. Outcomes will also be measured at the caregiver and community levels.

Enrollment is expected to take 1 month. Study participation will last 1 year.

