Participating caregivers will receive a \$25 gift card to the local store for each data collection visit for each participating child. There will be a \$50 bonus gift card if the caregiver participates in all 5 data visits (maximum total per child is \$175). After the main study period, caregivers from the control group who agree to continue participating will receive a \$50 gift card for each data collection visit for each participating child. Families in the two intervention communities will receive free samples of sugar-free water enhancers and vouchers that can be redeemed at the store. Vouchers will not be used in the control community intervention. During the data visits, children will receive a small gift (backpack, water bottle with study logo, study t-shirt, colorful cups, crazy straws). Families and children will also receive fluoride toothpaste and toothbrushes at each visit. In case of Covid-19 restrictions, all these items may be mailed to families instead of providing them in person. Additional retention strategies include maintaining contact with families between visits by creating a closed Facebook page, sending the children birthday cards, and texting and Facebook messaging families visit reminders, which is possible because nearly all families own a cell phone and use texting and Facebook as ways to communicate (see Manual of Procedures).

To minimize loss to follow-up and missing data, attempts will be made to contact participants by phone before all study visits. Often times, it is possible to contact difficult-to-reach individuals in the YK Delta by contacting a close relative, friend, or neighbor – for instance, if a cell phone has become temporarily disconnected. The data collected at baseline will include contact information of a close relative, friend, or neighbor who the study team is given permission to contact in the event a participating

caregiver cannot be contacted. Up to a 7-day period window will be allowed for data collection visit 1 and a 1-month-period for each subsequent data collection visit until an individual is considered to have missing data for that particular visit. An individual will be considered lost to follow-up if he or she fails to return for 3 consecutive data collection visits and is unable to be contacted by the study staff during the times at which the staff are in the communities for data collection.

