#### **4.5.2 Handling of Participant Withdrawals from Study or Participant Discontinuation of Study Intervention**

For participants who chose to withdraw from the study, or participants who chose to discontinue the study intervention, attempts will be made to collect the reason why. The reasons stated will be documented along with the date on which the participant withdrew or discontinued. Data collection will continue for participants who chose to discontinue the study intervention but chose not to be officially withdrawn (i.e., they would be willing to participate in data collection, but not the intervention). The study will not replace lost or withdrawn participants.

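### Reasons for dropout choose between multiple imputation and the non-ignorable sensitivity analysis; they cannot settle that choice, so both analyses should always be reported

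*Combined protocol and SAP*

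**What the plan says.** All references are to the combined protocol and SAP.

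- **Primary analysis (13.1).** "Linear regression analyses will be used to test if the average change in added sugar intake between baseline and 6 months is the same" in the two arms. The model is fitted by GEE with robust standard errors for household clustering, at a two-sided 0.025 level.
- **Missing data (13.1).** The section first points to 4.3 for how missing data are managed. Of the reasons for discontinuation and withdrawal it then says: "This information will be used to assess whether there is non-ignorable nonresponse". If nonresponse is found to be non-ignorable, a sensitivity analysis by weighted estimating equations looks at how the estimated effect moves "over a range of plausible values for the nonresponse mechanism". The alternative follows: "Otherwise, multiple imputation methods will be used to account missing outcomes".
- **Whose reasons (4.5.2).** For those who withdraw or stop the intervention, "attempts will be made to collect the reason why". The two groups differ: "Data collection will continue for participants who chose to discontinue the study intervention", provided they have not withdrawn from the study.
- **Missed visits (4.3).** Each data visit has a window "until an individual is considered to have missing data for that particular visit". The section asks for no reason at that point. It covers retention and the definitions of missing and lost to follow-up, and gives no analysis method.
- **Masking.** Sections 4.4.2 and 17.3 plan to mask the statistician. The Study Design section says of this attempt that "it will likely not be effective because of the different sizes of the intervention and control groups".

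**The concern.** The plan uses an assessment of the missingness mechanism as a switch between methods. Whether nonresponse is ignorable depends on the values that are missing, so the observed data fit equally well with many departures from missing-at-random. Stated reasons make some departures more plausible than others. They cannot show that there is none.

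The reasons also do not line up with the missing outcomes. Some children with a reason on file (those who stopped only the intervention) may still give a 6-month hair sample. Some children without a 6-month sample may simply not have been seen in the window.

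Each branch leaves a gap. If nonresponse is judged ignorable, no departure from missing-at-random is examined. If it is judged non-ignorable, only a sensitivity analysis is named, and the handling of missing 6-month outcomes in the main estimate is not stated. The judgement has no criterion and no named decision-maker, and it may be made with knowledge of arm. At stake are the reported effect size, the confidence a reader can place in it, and an avoidable discretionary choice in the primary analysis.

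**Working it through.** No figure in the plan is disputed on this point. The arithmetic asks how much the unexamined departure could matter.

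**Inputs (Sample Size Considerations; 4.5; 13.1).** Baseline 193.0 g/day, SD 43.6; correlation 0.6 between baseline and 6 months; 136 and 56 children; 2.15 children per household, SD 1.23; IFC 0.3 or 0.5; alpha 0.025 two-sided (critical z 2.24). Attrition is 15–25% for power, under 10% expected, and as low as 3% in earlier studies.

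**Step 1: standard error.**
- SD of change = 43.6 × √(2 × (1 − 0.6)) = 39.0.
- Design effect = 1 + ((cv² + 1) × 2.15 − 1) × IFC, with cv = 1.23/2.15 = 0.572. This gives 1.556 (IFC 0.3) and 1.927 (IFC 0.5).
- SE = SD × √(design effect × (1/136 + 1/56)/(1 − a)), where a is attrition.

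**Step 2: the plan's own power table.** With these inputs and 15–25% attrition, 20% v 2% at IFC 0.3 has power of about 94.5–97%, against 81% stated. The stated table is matched within about 2 points by an SD of change near 49 and 25% attrition. Both SDs are therefore carried below.

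**Step 3: shift in the estimate.** Assume that missing intervention children change like controls while imputation treats them like retained children. This is an upper case for that scenario if 1- and 3-month hair values inform the imputation. The difference then shrinks by a × difference. The differences are 193 × 0.18 = 34.74 g/day (20% v 2%) and 193 × 0.25 = 48.25 g/day (30% v 5%). With SD 39.0:

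| Attrition | SE, IFC 0.3 / 0.5 | Shift, 20% v 2% | in SE | Shift, 30% v 5% | in SE |
|---|---|---|---|---|---|
| 3% | 7.84 / 8.73 | 1.04 | 0.12–0.13 | 1.45 | 0.17–0.18 |
| 10% | 8.14 / 9.06 | 3.47 | 0.38–0.43 | 4.83 | 0.53–0.59 |
| 15% | 8.38 / 9.32 | 5.21 | 0.56–0.62 | 7.24 | 0.78–0.86 |
| 25% | 8.92 / 9.92 | 8.69 | 0.88–0.97 | 12.06 | 1.22–1.35 |

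**Step 4: significance after the shift.** z = difference × (1 − a)/SE.
- SD 39.0: the lowest z across the six power-table rows is 34.74 × 0.75/9.92 = 2.63 (20% v 2%, IFC 0.5, 25% attrition). At 10% attrition the lowest is 34.74 × 0.90/9.06 = 3.45. All exceed 2.24.
- SD 49, IFC 0.5, 25% attrition: SE = 12.47. For 20% v 1%, 193 × 0.19 = 36.67, and 36.67 × 0.75/12.47 = 2.21. For 20% v 2%, 34.74 × 0.75/12.47 = 2.09. Both fall just below 2.24.
- SD 49, IFC 0.5, 10% attrition: SE = 11.38, and the lowest z is 34.74 × 0.90/11.38 = 2.75. No row is lost.

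**Step 5: tipping point, 20% v 2%, SD 39.0.** Required departure = (34.74 − 2.2414 × SE)/a.
- At 10% attrition (about 14 of 136 children), missing intervention children would have to do 144–165 g/day worse than retained ones.
- At 25% (34 children), they would have to do 50–59 g/day worse. Retained children fall by 193 × 0.20 = 38.6, so intake in the missing children would have to rise by 11–20 g/day.

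**The case against.** The strongest reply is that little turns on this. The sponsor expects attrition below 10%, where the illustrated shift is at most about 0.6 SE and the tipping point is implausible against a baseline mean of 193 g/day. Data visits are separate from intervention visits and paid, and families may stop the intervention and stay in follow-up. This stands, and it limits the size of the point.

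Next, the plan only says that reasons will be used to assess nonresponse, and it already names both a missing-at-random method and a non-ignorable one. That is fair: no method is absent. But the assessment decides which method is used, so the gap on each branch remains.

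A reader might infer that reasons for missed visits are never recorded. The documents do not support that. Section 17.5 treats participant noncompliance as a deviation to be addressed in source documents, and the Manual of Procedures, which is not available here, may ask for a reason. Neither clearly guarantees one for each missed 6-month visit.

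A reader might also infer that the choice will certainly be made unmasked. Sections 4.4.2 and 17.3 plan masking; the Study Design section doubts that it will work. The supported statement is that the choice may be made with knowledge of arm.

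**Conclusion.** The point holds, at minor to moderate size, and the text should be changed. A judgement that reasons cannot settle, with no stated criterion, decides how missing 6-month outcomes are handled and whether any departure from missing-at-random is examined.

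Two stronger readings are not supported. One is that missing data threaten the trial's conclusion: under the scenario shown, significance is lost only in two low-effect rows, at 25% attrition, IFC 0.5 and an SD near 49. The other is that significance is safe in every planned scenario: that is true only with the SD of 39.0 from the stated inputs, which does not reproduce the plan's own power table.

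The figures assume equal attrition in both arms, a departure in the intervention arm only, and the effects used for power. They include no extra imputation variance and no between-community variance, although there is a single control community. A smaller true effect would make the shift matter more for significance.

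**What to change.** Delete the conditional in 13.1 and replace it with the following.

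1. Always use the plan's multiple imputation for missing 6-month outcomes in the primary analysis. The imputation should respect household clustering and use arm, baseline and the 1- and 3-month hair values that are already collected.
2. Always report the plan's named augmented inverse-probability-weighted sensitivity analysis for the primary outcome, over a pre-stated range that may differ by arm. A shift or tipping-point analysis may be added, but should not replace it.
3. Use recorded reasons, including those for missed 6-month visits where they exist or can be recovered, only to judge which values in that range are plausible.
4. Date the change before the analyst sees outcome data by arm.

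The cost is SAP wording and limited extra analysis: imputation that allows for households, and a sensitivity analysis now run on one branch only. Sample size, alpha and visits do not change. The 12-month form in Appendix T is dated September 2023, so 6-month visits may be past and some reasons may be unrecoverable. Items 1 and 2 do not depend on them, but that timing makes item 4 important.
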